## Protocol

### Abstract

We have designed a Cluster Cross-over pragmatic randomized controlled trial CCXOPRCT to test an intervention for a population seldom studied—hospice family caregivers—targeting an identified need (decision-making), and measuring a core set of caregiver outcomes (anxiety, pain knowledge, and patient pain). This will be the first shared decision making intervention in the hospice setting. This project proposes an intervention for hospice family caregivers called ACCESS (Access for Cancer Caregivers to Education and Support for Shared decision-making). Our preliminary work (R01NR011472) found that it is feasible to use web-based conferencing to facilitate family caregiver attendance at the hospice care plan meetings. Qualitative feedback indicates this attendance is beneficial to family members. However, we conclude that simply enabling attendance at these meetings is not sufficient to change clinical outcomes. For caregivers' anxiety to be changed they need to be prepared for these encounters and actively engaged with the hospice staff in shared decision-making. There is a critical need to arm hospice family caregivers with necessary information and a strengthened emotional state so they may become decision-makers. We propose using the Facebook platform to improve emotional support and caregiver knowledge to better prepare caregivers for participation and decision-making.

A CCXOPRCT design initially randomly assigns hospice sites to two of three groups: 1) Group 1 participants will serve as the control and receive usual hospice care enhanced by hospice staff training in shared decision making, 2) Group 2 participants will receive enhanced usual care as well as participate in a private Facebook support group to increase their knowledge and provide social/emotional support, 3) Group 3 participants will receive enhanced usual care, participate in the Facebook support group, and participate in hospice team meetings with a shared decision making process. After 12 months the group goes through a 90 day (or less if all have completed the trial earlier) washout period so all participants can complete the study. The group then is assigned to a second arm of the study for another 12 months. Again following a washout period so all participants complete the trial and then re-assignment to their first study arm again. Each cluster will go through two arms of the intervention, although participants will only complete one arm. A schedule has been developed. We will use qualitative and quantitative methods in parallel and equal status to measure the efficacy of the intervention.

**Our overall hypothesis is that ACCESS will improve hospice cancer family caregiver knowledge and emotional state (via Facebook), thereby facilitating a shared decision making process, which will result in improved caregiver anxiety and knowledge and improved pain control for patients.**

### Objectives

We have three specific aims: 1) Evaluate the effect of ACCESS on hospice family caregiver anxiety, pain knowledge, and patient pain; 2) Evaluate the effect of social media as a decision aids and decision support for pain management by family caregivers; 3) Evaluate the satisfaction of staff and family caregivers with a shared decision making process for pain management and patient care.

## **Background**

The Institute of Medicine reports 40% of patients at the end of life have severe, unrelieved pain. Those dying of cancer carry a disproportionate burden of the likelihood of dying in pain. Unrelieved pain has been attributed to inadequate communication between providers, caregivers, and patients. Pain management and family caregiver (FCG) support are core components for quality end of life care, and with 78% of FCGs of cancer patients administering an average of 5-9 medications per day, including narcotic medication for pain, the burden on families is tremendous. Caregiving takes a toll when the family member worries about performing tasks safely, especially when their loved one is in pain. Although FCGs show concerns about reporting pain to health care teams and administering pain medications to their dying loved ones, many health care providers fail to address these concerns. Research has found that pain management is especially troublesome for FCGs of cancer patients, causing them anxiety and distress related to the administration of narcotics. As one participant in our preliminary trial stated, "I'm not a doctor, and I do not know if I helped her go faster or slower or what, hell I do not know." This project addresses the anxiety of FCGs of hospice cancer patients by involving them in shared decisions related to managing pain at the end of life.

Although frequency and type of adverse effects vary, our studies find that one-third of FCGs of hospice patients are moderately to severely anxious, and more than one-half are depressed. Given the number of patients at the end of life who experience pain, the challenges experienced by FCGs who manage their pain, and the resultant FCG anxiety, the IOM suggest that FCGs should be integrated into the health care team and be provided training and support. However, hospice FCGs and patients are routinely absent from the care plan meetings where key decisions are made. When FCG input is lacking, care plans suffer from incorrect assumptions about the patient and family perspectives. We have pilot-tested implementing the IOM recommendation for family involvement in the hospice interdisciplinary care plan meeting. This meeting is required by Medicare conditions of participation and occurs every 14 days for each patient. While these meetings can offer opportunity for family integration with the hospice team and have potential to facilitate shared decision-making, it is not common practice to include FCGs in hospice care planning meetings.

Shared decision-making (SDM) is a process wherein a healthcare choice is jointly made by a healthcare provider (in this case, hospice) and a patient and/or patient's proxy (FCG). While hospice principles support SDM, evidence for SDM in the hospice setting does not exist. To test the feasibility of FCG participation in hospice care plan meetings, we have recently completed an extensive preliminary trial, using web conferencing to facilitate FCG attendance of hospice team care plan meetings (R01NR011472). We demonstrated the feasibility of including FCGs in meetings through web-conferencing. We found FCGs lacked the knowledge to fully understand providers and often used meeting time to seek information and emotional support. We also found that FCG anxiety and patient pain are correlated and FCGs of hospice cancer patients reported higher anxiety and higher patient pain than FCGs of non-cancer patients, leading us to focus on cancer patients and their FCGs.

## **Study Procedures**

We propose an intervention to target education and emotional support to FCGs based on a structured process for SDM. ACCESS (Access for Cancer Caregivers to Education and Support for Shared decision- making) has three components; 1) Facebook groups to provide education and emotional

support to FCGs, 2) web-conferencing to involve FCGs in care plan meetings and, 3) a structured SDM process to guide team discussion. These components will facilitate SDM between the hospice staff and FCGs, lower FCG anxiety, and increase FCG knowledge regarding patient pain, resulting in less pain for cancer patients. A pragmatic cluster randomized controlled trial (PC-RCT) will randomly assign hospice sites to one of three groups: FCG participants at Group 1 sites receive only enhanced usual care (EUC), FCG participants at Group 2 sites receive EUC and participate in Facebook (FB) groups for informational and emotional support, FCG participants at Group 3 sites receive EUC, participate in Facebook groups and the interdisciplinary team meeting for SDM (FB/SDM). Usual hospice care will be enhanced through education on SDM for all staff.

This study will last five years. Participants will be in the study for up to 120 days, depending on the death or discharge of their patient. Team meetings are held every other week, Facebook groups will be visited at least two times per week. Data collection will be done on the following schedule: baseline (day one), day 14, day 30, day 60, day 90, and on or before day 120. Data collection may end earlier at 14-21 days after the death or termination of the patient from hospice services or if a study volunteer chooses to end their participation. A qualitative interview will be done on or around the same day that the last quantitative measures are gathered.

We propose a pragmatic cluster randomized three-group design with a mixed methods analysis where qualitative and quantitative data are collected at the same time and given equal status in evaluating the effectiveness of the intervention. We propose a pragmatic trial rather than an explanatory trial because by testing ACCESS in a real-world context we will be able to determine if it will reduce FCG anxiety, improve FCG knowledge of pain, and reduce patient pain. This trial is considered pragmatic because 1) it has broad inclusion criteria, 2) hospice staff are not told how to apply the intervention, 3) the intervention is applied by the entire hospice team, 4) the Enhanced Usual Care (EUC) training on SDM will be given to all hospice clinical staff and all participants without restriction, 5) the primary outcome (anxiety) is a clinically meaningful one and does not require extensive training to evaluate, 6) compliance with either the intervention or EUC will not be monitored (although it will be documented), 7) there are no special strategies to motivate the hospice staff adherence to SDM, and 8) the analysis will include all participants in an intention-to-treat fashion. EUC as a comparator is appropriate when the goals of a trial are pragmatic rather than explanatory. A mixed-methods approach will involve conducting statistical analyses of measures supplemented by qualitative analysis of video-recorded team discussions, Facebook data, and interviews.

## **Inclusion/Exclusion Criteria**

**Exclusion/Inclusion Criteria:** FCGs are the focus of the study. They must be at least 18 years of age, involved in daily decisions related to the patient's care, and be a designated family/friend caregiver for a cancer patient enrolled in a participating hospice. Subjects must be willing to use or set up an email account. Participants in Group 2 must further be willing to use a Facebook account. Participants in Group 3 must be willing to use a Facebook account and video conferencing (VSee). FCGs without an Internet-enabled device will be supplied with a smartphone and data plan (restricted to Facebook posting, answering study correspondence and surveys, and care planning meeting time) for the duration of their participation.

Caregivers are the focus of the study, and as many hospice patients are too ill to participate they will not be enrolled. The inclusion criteria include a terminal cancer diagnosis for the care recipient, enrolled in the participating hospice, and a FCG at least 18 years of age (to reflect the typical hospice patient population) willing to use the required technology. Patients of FCGs must have a likely life expectancy of more than two weeks as determined the hospice nurse.

Hospice staff (e.g., nurses, social workers, physicians), also study subjects, must be employees of participating hospices and be at least 18 years of age to be included in the study.

## Randomization

We will use a cluster randomization design because:

1. Our aims contain individual level and organizational level outcomes. Study aim 3 can then be assessed at the organizational level as well as the individual level.
2. Given the large geographic distance covered by the six participating hospice sites, it is far more cost effective to focus our intervention costs at specific hospice sites rather than across all sites. This will allow us to assess the total impact of an agency wide intervention. In keeping with the pragmatic goal of our trial this is more reflective of how implementation would actually be done at a hospice site, as individuals would not be given random interventions in real life.
3. We will avoid the contamination between the intervention groups and the control group- an unavoidable consequence of having both groups in one hospice site. We believe contamination may have lowered our ability in the pilot study to detect the change in the primary outcome.
4. These sites provide us with a diverse sample. We will have rural and urban hospice programs, a greater number of under represented minorities, and a more diverse hospice staff.

We have chosen a cross over design to increase precision as each arm of the study may serve as its own control group, thus reducing the number of participants necessary to have adequate power. This has been the recommended design for small numbers of clusters that are not meeting recruitment goals.

## Recruitment

The hospice agency will include a flyer about the study in their admissions packets. They will also include an opt-out form, allowing individuals to note that they do not want the research staff to contact them with information about the research. Hospice staff will refer all other caregivers to the research staff. Research staff will call or email and establish a time to explain the study and offer FCGs the opportunity to participate. Participants will verbally consent to participate and baseline measures will be obtained via telephone. It is anticipated that the data will be entered directly into REDCap as the survey is performed, thus preserving anonymity. Participants may choose to have follow-up measures over the phone or electronically, except for Group one where telephone contact will be continued as a way to maintain engagement and reduce losses to follow-up. The waiver of documentation of consent will be emailed to each participant. As needed, participants will be assisted with setting up and using email addresses, Facebook accounts, smartphones, and VSee.

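### The follow-up mode rule for GAD-7 differs between Group 1 and the two intervention groups and no planned analysis addresses it; separately, and less seriously, the covariate plan rests on an individual-randomisation premise that the design does not meet.

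*Combined protocol and SAP*

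**What the plan says.** **Mode.** Under Recruitment, "baseline measures will be obtained via telephone" in every group. At follow-up, "Participants may choose to have follow-up measures over the phone or electronically, except for Group one where telephone contact will be continued"; the reason given for Group 1 is "as a way to maintain engagement and reduce losses to follow-up". Study Statistics says only that research specialists collect all data through REDCap, by phone, or both. GAD-7 is named as the primary outcome in the list of caregiver measures.

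**Allocation and entry.** Study Procedures will "randomly assign hospice sites to one of three groups". The Abstract describes a cross-over of sites: "The group then is assigned to a second arm of the study for another 12 months". Each caregiver completes one arm only. Under Inclusion/Exclusion Criteria, all caregivers must accept email. Beyond that, "Participants in Group 2 must further be willing to use a Facebook account", and Group 3 must accept Facebook and video conferencing. A phone and data plan are supplied where needed.

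**Analysis.** The model in Statistical Analysis H1- H3 has terms for study group, baseline measure and time since enrollment. Statistical Analysis expects confounders to balance because individuals are randomised. It adds other covariates only when a baseline chi-square or t-test is significant. All outcome analyses are by intention-to-treat.

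**The concern.** H1, the enhanced-usual-care part of H2, and H3 all compare GAD-7 with Group 1. Anxiety reported aloud to a research specialist may be answered differently from anxiety typed into a form. If so, the difference enters the estimated effect in 2 v 1 and 3 v 1, and no planned analysis separates it. It could imitate a benefit or hide one.

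The second part concerns who enters. Sites are allocated first, and the technology requirement then depends on the arm, so balance between caregivers cannot be assumed from randomisation. Covariates that enter only after a significant baseline test will often be left out when a modest imbalance is present.

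**Working it through.** **1. Does any planned step reach mode?**
- Baseline GAD-7: no. All baselines are by telephone, so the baseline carries no information on a mode shift at follow-up.
- The covariate rule: no. It screens baseline variables, and follow-up mode is not one.
- The model: no. It has no mode term.
- The cross-over: no. When a site enters or leaves Group 1, the mode rule changes with the arm.
- Intention-to-treat: no. It governs who is analysed, not how the outcome is measured.

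In 3 v 2 both groups have the same choice, so the rule does not differ there.

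**2. How large could a mode bias be?** The documents give no SD, intracluster correlation, electronic share or mode effect, so there is no plan figure to reproduce. Everything below except 642 is assumed.
- n per arm: 642 interviews (Qualitative Data) in equal thirds, 642/3 = 214.
- SD 5; baseline to follow-up correlation r = 0.5 or 0.7; design effect (DE) 1 or 2; two-sided 5% test.
- SE0 = 5 x sqrt(2 x DE/214) = 0.483 (DE 1) or 0.684 (DE 2).
- Adjusted SE = SE0 x sqrt(1 - r^2): 0.419 and 0.345 (DE 1, r = 0.5 and 0.7); 0.592 and 0.488 (DE 2).
- Mode bias = share electronic x shift in points, not reduced by baseline adjustment.
- Error rate with no true effect = P(|Z + bias/SE| > 1.96).

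| Share x shift | Bias (points) | Error rate, DE 1 (r = 0.5 / 0.7) | Error rate, DE 2 (r = 0.5 / 0.7) |
|---|---|---|---|
| any share x 0, or 0 x any shift | 0 | 5% | 5% |
| 0.3 x 0.5 | 0.15 | 6.5% / 7.2% | 5.7% / 6.1% |
| 0.5 x 1.0 | 0.50 | 22.3% / 30.5% | 13.5% / 17.6% |
| 0.8 x 1.5 | 1.20 | 81.8% / 93.5% | 52.7% / 69.1% |

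The last row stacks two extreme assumptions. With half the sample (107 per arm) and DE 2, the 0.5-point bias gives 9-11%.

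**3. How large could the selection part be?** Assume refusers differ by the same amount at baseline and follow-up. The residual after baseline adjustment is then (1 - r) x share refusing x difference.
- 30% refusing and a 2-point difference: raw 0.6; residual 0.30 (r = 0.5) or 0.18 (r = 0.7); error rate 11.1% or 8.2% (DE 2: 8.0% or 6.6%).
- Raw 0.3: residual 0.15 or 0.09; error rate 6.5% or 5.8%.
- For 3 v 2, 15% refusing video and a 2-point difference also give raw 0.3, so at most about 6.5%.

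**4. What does the significance screen cost?** At 214 per arm the observed imbalance must reach 1.96 x sqrt(2/214) = 0.19 SD to trigger adjustment (0.27 SD at DE 2). A true imbalance of 0.2 SD is flagged 54% of the time (31% at DE 2). Missing it costs little, however. In a simulation of one measured covariate (4,000 trials per setting, no clustering, imbalance 0.1-0.3 SD, covariate slope 0.2 or 0.4), the screen left a bias of 0.004-0.024 SD and a null rejection rate of 4.6-5.3%. With no adjustment at all the bias was 0.018-0.120 SD. Always adjusting left at most 0.002 SD.

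**The case against.** The Group 1 rule has a sound purpose: calls retain caregivers who have no Facebook or meeting contact. That explains calling Group 1. It does not explain leaving mode unequal elsewhere or out of the analysis.

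A reader might infer that mode and arm coincide, or that GAD-7 is shown to be biased in favour of ACCESS. The documents support neither. Groups 2 and 3 may also choose the telephone, and nothing shows that mode shifts GAD-7 answers. The larger error rates come wholly from assumed inputs. The DE 2 column also presumes a standard error that allows for clustering, whereas the stated model nests repeated measures within participants only.

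A reader might also infer that the differing entry criteria have made the groups unequal, or that the covariate screen seriously inflates error. No imbalance is shown, phones and set-up help are supplied, and baseline GAD-7 and time are always in the model. The simulated cost of the screen is small for a measured covariate. This objection largely stands, and it makes the selection part minor. Pre-named demographics would not remove selection on technology willingness either, since no listed measure captures it.

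Nor do the documents show that refusals go unrecorded. Staff document opt-outs, and no log of refusals after the research call is described. The survey attachments were not available, so mode may already be recorded.

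**Conclusion.** The mode point holds and is worth fixing: the rule for measuring the primary outcome differs by arm in both contrasts with Group 1, and nothing in the plan equalises or analyses it. Its size and direction are unknown. It may be zero, and the calculated rates show only that a moderate share and shift would matter at this sample size.

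The covariate point holds in a limited form. The premise of individual randomisation contradicts the site allocation in the Abstract, Study Procedures and Randomization, and pre-named covariates are a better method at almost no cost. The gain for any one measured covariate is small, and selection on unmeasured willingness remains under either rule.

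**What to change.** 1. **Recruitment.** Make telephone the default follow-up mode for GAD-7 in all three groups. Allow electronic completion only as a fallback, offered equally in every group when a call cannot be completed. Record mode at each assessment and report it by arm.
2. **Statistical Analysis H1- H3, for data already collected.** Pre-specify a mode sensitivity analysis that keeps all participants: shift electronic GAD-7 values over a stated range and report where the conclusion changes. State that mode was self-chosen and varies only in Groups 2 and 3. Do not rely on excluding electronic values, which conditions on a choice made after allocation and can move the last observation earlier. Do not rely on the post-death GAD-7, which measures a different state.
3. **Statistical Analysis.** Delete the individual-randomisation premise. Replace significance-triggered covariates with a short pre-named set in every model: baseline score, time to last observation, age and key demographics already collected.

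Reporting refusals by arm, site and period would be useful added detail, but is not essential.

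**Cost.** A protocol amendment and, if not already present, one mode field. Groups 2 and 3 hold 2 x 214 = 428 caregivers with up to 5 follow-ups each. If 30-80% would have chosen electronic, the extra calls number at most 428 x 5 x 0.3 = 642 to 428 x 5 x 0.8 = 1,712. If 75% leave by day 90, as in the preliminary trial, and so have at most 4 follow-ups, there are 428 x (0.75 x 4 + 0.25 x 5) = 1,819 assessments, or 546-1,455 calls. Existing research specialists would make them. The drawbacks are possible added burden or loss in Groups 2 and 3, and more answers given aloud to staff who also run the Facebook groups. If only GAD-7 moves to the telephone, the other outcomes keep the same mode difference.

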## Intervention

Table 1 summarizes the intervention design. Details are included below.

Table D.2.1 Summary of Theoretical Components, Intervention, Components, and Design				
Intervention component	Theoretical component (outcome)	Group 1 EUC	Group 2 FB	Group 3 FB/SDM
Usual hospice care (philosophy, visits, team meets every 14 days)	Organizational structure (non-profit vs for profit, rural vs urban)	x	x	x

Enhanced usual hospice Staff training in SDM process	Team Process(staff knowledge SDM)	x	x	x
Pain education via Facebook support group shared resources and peer discussion	Team Process: Communication Climate (pain questionnaire)		x	x
Emotional support via Facebook peer support group	Team Process: Communication Climate (general anxiety)		x	x
Structured SDM process in team meeting	Team Process(9 step SDM process in meeting)			x
Participation in team SDM	Team Structure(FCG participation with team)			x

**Group 1: Enhanced Usual Care Group:** Participants in this group will receive usual hospice care that does not include participation in a Facebook support group or the ability to participate in team SDM via web-conferencing. The enhanced care is a result of the staff training in SDM.

**Group 2: Secret Facebook Group:** Research specialists will train FCGs assigned to Group 2 and Group 3 (Facebook or Facebook + SDM groups) to use Facebook. They will demonstrate how to adjust privacy settings and use Facebook. FCGs will also be given a printed guide to Facebook (including Rules of Conduct) as a reference. Research specialists will assist FCGs with their first post, which will introduce them to the group. Secret Facebook groups are not searchable on the Internet, and only members authorized by the administrator can view what is shared. Research Specialists will serve as administrators. We will create a secret Facebook group for all participants randomized to either Group 2 or 3 in each hospice. Participants will be asked to log onto Facebook at least twice weekly and read the content. They are encouraged, but not required, to respond. [name] (co-investigator) will monitor all Facebook groups to provide continual assessment of emotional distress and compliance with rules of conduct. Hospice staff will not be a part of the Facebook groups to ensure intervention fidelity across intervention arms.

As in our pilot study, research specialists will monitor discussion daily via Facebook notifications, with support from Drs. [name]. Weekly, research specialists will post a link to vetted pain information and other resources to their Facebook group, and provide a discussion question. Previous postings will be available to new members for a set period of time. In our pilot work, resources and discussions increased pain knowledge of FCGs and generated peer emotional support as FCGs shared their common caregiving challenges and emotions. Guidelines for participation detail rules of conduct, including that participants will not give medical advice, and will not be critical of one another. Guidelines were honored in the pilot without concern. The research specialists will communicate FCG concerns to hospice staff in an agreed upon manner (text, email, etc.).

Although Facebook is an excellent platform for delivering educational content, it is important to address the ethical issues of monitoring the accuracy of information and protecting group members from unintentional disclosure. We have dealt with these issues in Section E of the proposal, which describes our policy and procedures for managing anticipated privacy concerns. Before posting links, clinical accuracy of material will be verified by Co-Investigator [name] (a national leader and

board-certified physician in hospice and palliative medicine), [name] (radiation oncologist), and [name] (APRN, PhD). When FCGs have clinical questions or concerns, research specialists will forward them to hospice nurses or medical directors for response via traditional methods.

**Group 3: Facebook+ SDM:** Individuals assigned to this group will receive the Facebook intervention and will additionally attend the bi-weekly hospice team meeting (via web-conferencing) to participate in SDM. They will be trained on use of the web-conferencing software, the purpose of the team meeting, and how best to prepare for participation. Training will include how to create a list of problems, questions, and requests in advance, using the 9-step SDM process, and how to identify items appropriate for the meeting versus items appropriate for staff home visits. As in our preliminary trial, we will use web conferencing tool VSee to connect intervention-group FCGs with biweekly care plan meetings. On the day before the meeting, the hospice will provide our research specialist a list with the order for patient care plan discussions. This will allow research staff to estimate the time when study participants will be discussed and provide FCGs with a time estimate so they can be ready for the conference. Research staff will notify them via email or text message during the meeting about any delays. A projector allows the visualization of the FCGs and hospice team members on a large screen in the team meeting room, facilitating both verbal and non-verbal communication as the group discusses the care plan. The technology allows multiple users to participate, and additional providers or FCGs can join the meeting. This approach, which mirrors our preliminary trial, has worked well and proven satisfactory to staff and FCGs. Although FCGs and staff report benefits from video images, telephone conferences will be used in cases of technical difficulty with the video-conferencing.

